## DATA COLLECTION PROCEDURES

**Neural Recording Procedures:** The proposed study design will enable synchronized recordings to be made in the form of LFP from the six or eight channels of implanted DBS lead(s), as well as IMU sensors from the V-GAIT platform to quantify gait-related behaviors using a commercial EEG recording platform. The physiological and sensor data will be synchronized to motor task and gait-related activities and events associated with participant performance on the V-GAIT paradigm through additional analog and digital ports using a low voltage electrical current (1.5 mA) through surface electrodes placed on the participant's neck.

**Behavioral Tasks:** The Unified Parkinson's Disease Rating Scale (UPDRS) will be conducted by a rater blinded to medication state.

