## **DATA ANALYSIS**

**Biomechanical Data Analysis:** All data will be recorded and analyzed off-line using custom-scripts in Matlab using the Chronux toolbox to examine changes in oscillatory neural activity time-locked to FOG episodes identified with the kinematic data from the body worn motion sensors in the motion capture area. The 3D position data of each foot will be utilized to determine steps and other biomechanical stepping variables FOG episodes will be identified utilizing the data from the body-worn motion sensors.

**Neural Data Analysis:** Neural data will be detrended and passed through a moving window line noise subtraction algorithm to remove drifting baseline and continuous noise artifacts, respectively. From the Percept device, 6 electrode pair combinations, 3 combinations per DBS lead, will be recorded directly with the Percept communicator. Windows containing movement artifacts will be visually identified by large fluctuations in the time series and high amplitude broadband activity in the spectrogram and removed from further analysis. Triggered spectrograms will be calculated for each trial using the multi-taper method with a 100 ms, 50 ms overlap moving window, 2.5 Hz frequency resolution, and 1 taper.

**Local Field Potential (LFP) Outcomes:** The relationship of synchronization and desynchronization changes in oscillatory activity within the delta, theta, alpha, beta and/or gamma bands as well as the power of high-frequency oscillations (200+ Hz) will be calculated in relation to all events identified with the kinematic data, i.e. normal walking and FOG episodes. Power spectral densities will be used to determine the power and confidence bands of oscillatory activity across frequencies during these events.

**Statistical Analysis:** Neural data outcomes, average power within alpha, beta, and/or gamma frequency bands, will be quantified using descriptive statistics during FOG episodes and during periods of functional walking while performing the V-Gait modules. Within and across participant analyses will determine the degree of consistency and similarity of the neural signal during FOG episodes between each medication state (ON and OFF).

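### The artefact rule does not address small movement-locked components, so a low-frequency FOG–walking difference could not be separated from movement if such components are present

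*Combined protocol and SAP*

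**What the plan says.** All points are from DATA ANALYSIS unless noted.

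- **Cleaning.** The neural data are "detrended and passed through a moving window line noise subtraction algorithm to remove drifting baseline and continuous noise artifacts, respectively". Windows with movement artefact are then "visually identified by large fluctuations in the time series and high amplitude broadband activity in the spectrogram" and dropped. No numeric threshold is given.
- **Spectral settings.** Triggered spectrograms use the "multi-taper method with a 100 ms, 50 ms overlap moving window, 2.5 Hz frequency resolution, and 1 taper". The window for the separate power spectral densities is not stated.
- **Outcomes.** The LFP Outcomes paragraph looks at activity "within the delta, theta, alpha, beta and/or gamma bands", plus high-frequency oscillations. The Statistical Analysis paragraph is narrower: "average power within alpha, beta, and/or gamma frequency bands", which "will be quantified using descriptive statistics during FOG episodes and during periods of functional walking". Alpha is in both lists; delta and theta are only in the first. No band edges are given.
- **Labelling.** FOG episodes are found from the body-worn motion sensors.
- **Available reference.** Under DATA COLLECTION PROCEDURES, the LFP is synchronized with "IMU sensors from the V-GAIT platform to quantify gait-related behaviors". METHODOLOGY AND APPROACH places the sensors on the head, waist and both feet. The plan does not use them to check the LFP for artefact.

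**The concern.** The plan expects movement artefact, but both of its markers describe gross events. A component at the step rate, or at a trembling rate during a freeze, is narrow-band and may be small. It would match neither marker, and neither detrending nor line-noise subtraction is aimed at it.

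This is more than added noise, because the two states are defined by how the person moves. A retained movement-locked component is therefore tied to the FOG–walking contrast, which is the one that answers the Objective. With 15 participants, descriptive summaries and no control analysis, nothing in the plan would reveal it. A movement difference could be reported as part of the neural signature of FOG, or could mask a real one. If the component also differed by medication state, the ON–OFF comparison would be touched too. That last step is conditional and has not been quantified.

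**Working it through.** The plan gives no figure to reproduce, so the check has two parts: would the rule see such a component, and what would the component do to the contrast?

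**Inputs from the plan:** 100 ms window, 50 ms steps, one taper.

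**Assumptions, none from the documents:** 250 Hz sampling; a 1/f to 1/f^1.5 background with a beta peak, identical in both states; theta 4–8 Hz and alpha 8–12 Hz; stepping at 1.8 Hz during walking; trembling at 5.5 Hz during FOG. Residual size is the SD of the added component divided by the SD of the LFP.

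**1. Visibility.** Total SD relative to clean LFP = √(1 + r²), where r is the residual size.
- r = 0.3: √1.09 = 1.044, a rise of about 4%.
- r = 0.5: √1.25 = 1.118, a rise of about 12%.

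In simulation the 99.9th percentile of amplitude rises by about 3–6% at r = 0.3 and 9–13% at r = 0.5. A pure sinusoid of amplitude 0.5 SD moves gamma by no more than 0.01 dB. This is neither a large fluctuation nor broadband activity, so visual review would probably pass it.

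**2. Effect on the contrast.** Spurious change = (B + F)/(B + W) − 1. B is background band power, the same in both states; F and W are the band power added by the component in FOG and in walking. Simulated results for the planned 100 ms window:

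| Residual in FOG | Residual in walking | Theta | Alpha |
|---|---|---|---|
| 0 | 0 | 0 | 0 |
| 0.1 | 0.1 | negligible | +1 to +2% |
| 0.3 | 0.3 | near zero | about +12% (range +10 to +14%) |
| 0.5 | 0.5 | near zero | about +30% (range +24 to +33%) |
| 0.3 | 0.5 | −15 to −21% | 0 to +3% |
| 0.3 | 0.6 | −26 to −32% | −14% |
| 0 | 0.3 to 0.5 | −12 to −35% | −5 to −19% |

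Near zero means between −3% and +6% over repeat runs. The alpha ranges cover runs with and without harmonics; the 0.3 versus 0.6 row includes harmonics.

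**3. A second set of rates.** Take 6 Hz in FOG and 1 Hz in walking, pure sinusoids of amplitude 0.5 SD (residual 0.5/√2 = 0.35), 250 Hz sampling.
- Equal amplitudes: theta +0.2 dB, 10^0.02 = 1.05, or +5%; alpha +0.9 dB, 10^0.09 = 1.23, or +23%.
- Walking amplitude doubled to 1.0 SD: theta −1.7 dB, 10^−0.17 = 0.68, or −32%; alpha +0.2 dB, or +5%.

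**4. Which bands.** At amplitude 0.5 SD, over component rates of 1–8 Hz, delta rises by 0.4–1.6 dB and beta by up to 0.3 dB (at 8 Hz). The exposure therefore runs from delta to alpha, with slight leakage into beta.

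**5. Role of the window.** 1/0.1 s = 10 Hz, whereas 2.5 Hz resolution needs about 1/2.5 = 0.4 s. Much of the alpha shift is leakage from the short window. With a 1 s window, a pure 6 Hz sinusoid of amplitude 0.5 SD adds 2.4–3.0 dB to theta and only 0.01 dB to alpha.

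**The case against.** Four points count against this concern.

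- **Existence.** No document says that such components occur in these implanted recordings, and trembling is not mentioned at all. The 0.3 and 0.5 SD residuals have no source. This stands, and it makes the point conditional.
- **Size and sign.** A reader might infer that artefact will stay in the signal and show up as a raised theta and alpha signature of FOG. The documents do not support that. Large theta shifts (roughly +42 to +59% at 0.3 SD in simulations with harmonics) need a 1 s window. The plan does not state one, though the window for its power spectral densities is open. With the planned 100 ms window and equal residuals, theta hardly moves, and the direction reverses when walking carries more artefact.
- **Overlap with another issue.** Much of the alpha effect comes from the mismatch between the 100 ms window and the stated resolution. This also stands. A coherence check does not repair that mismatch, which needs its own correction.
- **Over-correction.** The study looks for neural activity linked to gait events, and regressing out sensor signals can remove it. This stands, and it rules out requiring a finding to survive regression.

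Theta and delta are also absent from the Statistical Analysis list, so within that paragraph the exposure is mainly alpha. None of this fills the gap: no stated step would detect or rule out such a component.

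**Conclusion.** The concern holds in conditional form. The visual rule is aimed at large, broadband artefact, and nothing else in the plan addresses low-amplitude components locked to stepping or trembling. Because motion separates the two states, a FOG–walking difference in delta-to-alpha power could not be told apart from such a component if one is present.

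Its presence, size and sign are unknown. The illustrative alpha shifts of about +12% and +30% rest on the assumed rates, equal residuals of 0.3 and 0.5 SD, and the planned 100 ms window. They show what could pass unseen and do not predict this trial's results. This is a worthwhile, inexpensive improvement; it does not show that the planned results will be biased.

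**What to change.** Add a short step after visual removal.

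1. For each channel and session, compute and report coherence between the LFP and the foot and waist sensor signals, separately for FOG and walking. State in advance how coherence will be judged present. Use segments longer than 100 ms for this, since that window holds only 1.8 × 0.1 = 0.18 of a cycle at the assumed step rate. Say where FOG episodes are too short to assess.
2. Where coherence is present, report the FOG–walking and ON–OFF band-power summaries with and without regression on lagged sensor signals (for example ±250 ms), as a sensitivity analysis.
3. Keep the unregressed result as the main one. Describe a low-frequency difference that disappears after regression as not separable from movement. Do not make agreement between the two versions a condition for reporting a signature.

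The cost is a few lines of analysis text and some extra offline processing of signals already recorded and synchronized, with no added burden for participants. The drawback is that the regressed version may also remove genuine gait-locked neural activity. If coherence proves negligible, the sponsor gains direct support for a neural reading of the result.

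### The triggered spectrograms are stated at 2.5 Hz resolution, but a 100 ms single-taper window resolves about 10 Hz, too coarse to separate delta, theta and alpha reliably

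*Combined protocol and SAP*

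**What the plan says.** All of the relevant text is in the DATA ANALYSIS section of the combined protocol and SAP.

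- **Neural Data Analysis** sets the parameters of the triggered spectrograms: "multi-taper method with a 100 ms, 50 ms overlap moving window, 2.5 Hz frequency resolution, and 1 taper".
- **Local Field Potential (LFP) Outcomes** lists changes in "oscillatory activity within the delta, theta, alpha, beta and/or gamma bands", together with high-frequency power, and says that these "will be calculated in relation to all events identified with the kinematic data, i.e. normal walking and FOG episodes".
- The same paragraph plans a second estimate: "Power spectral densities will be used to determine the power and confidence bands of oscillatory activity across frequencies during these events". No window length or taper is given for it.
- **Statistical Analysis** names the summarised outcome as "average power within alpha, beta, and/or gamma frequency bands". Delta and theta are not in that list, and the sentence does not say whether the spectrograms or the spectral densities supply the averages.

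The section gives no band limits, sampling rate, zero-padding or time-bandwidth product, and no separate longer window for low frequencies.

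**The concern.** Window length limits frequency resolution: a window of T seconds cannot resolve much finer than 1/T. A 100 ms window is a quarter of the length that 2.5 Hz calls for, so the stated resolution conflicts with the window and taper count in the same sentence.

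The project aims to find neural signatures of freezing of gait, and the triggered spectrogram is the only time-resolved method whose settings are given. Someone relying on 2.5 Hz would take delta, theta and alpha changes around an episode as distinct findings. If the true resolution is about 10 Hz, each of those bands is narrower than the response of the method, and a change in one spreads into its neighbours.

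**Working it through.** **Inputs.** From Neural Data Analysis: T = 0.100 s, number of tapers K = 1, stated resolution 2.5 Hz. Assumed, because the documents give none: delta 1-4, theta 4-8, alpha 8-12 and beta 13-30 Hz. Sampling rates of 250 and 1000 Hz were both tried, and the shares in step 3 agree to 0.1 percentage point.

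**Step 1. Can 2.5 Hz be reproduced?** Let W be the half-bandwidth.

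- Basic limit: 1/T = 1/0.1 = 10 Hz.
- Usual multi-taper rule, K = 2TW - 1: K = 1 gives TW = 1, so W = 1/0.1 = 10 Hz (full bandwidth 2W = 20 Hz).
- Forcing W = 2.5 Hz: TW = 0.1 × 2.5 = 0.25, and the rule gives K = 2 × 0.25 - 1 = -0.5, which is not a taper count. One taper can still be computed at TW = 0.25, but step 2 shows that it does not deliver 2.5 Hz.
- Bin spacing: padding the transform fourfold, to 0.4 s, gives 1/0.4 = 2.5 Hz. This matches the number, but as interpolation between points and not as resolution.
- In reverse: W = 2.5 Hz at TW = 1 needs T = 1/2.5 = 0.4 s. If 2.5 Hz means the full bandwidth, T = 2/2.5 = 0.8 s.

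**Step 2. Width actually delivered**, from the spectrum of the first Slepian (DPSS) taper.

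| Window | TW | Half-power width | Energy within ±2.5 Hz |
|---|---|---|---|
| 100 ms | 1 | 10.75 Hz | 43% |
| 100 ms | 0.25 | 9.0 Hz | 47% |
| 400 ms | 1 | 2.7 Hz | 98% |

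Against the stated figure, 10/2.5 = 4 times coarser.

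**Step 3. Where the power lands.** With H the taper's power spectrum scaled to total 1, a tone at f0 contributes to a band the integral of H(f - f0) + H(f + f0) over that band. Averaging over f0 gives the share for a source that fills a band. No background spectrum is needed. Power not shown falls outside the listed bands.

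| Source | 100 ms, TW = 1 | 400 ms | 1 s |
|---|---|---|---|
| 4-8 Hz | theta 34.5%, delta 24%, alpha 24% | theta 78%, alpha 11% | theta 91%, alpha 4% |
| 8-12 Hz | alpha 34%, theta 24%, beta 25% | alpha 78%, theta 11%, beta 3% | alpha 91%, theta 4%, beta 0.2% |

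- With TW = 0.25 at 100 ms, the 4-8 Hz source is 38% theta and 24% alpha, so the choice of TW does not rescue the separation.
- Equal tones at 6 and 10 Hz merge into one peak at 8 Hz at 100 ms, and give two peaks at 400 ms.
- A 3 Hz tone puts 39% in delta, 33% in theta and 11% in alpha, so delta against alpha is degraded but not lost.
- At 100 ms a 20 Hz tone keeps 94% in beta, a 15 Hz tone keeps 67% (20% goes to alpha), and a 60 Hz tone keeps at least 97% in gamma.

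**Step 4. Relative size of the false alpha change.** If a band receives source power S and background power B, doubling the source raises the band by S/(B + S). This step does need a background, which the documents do not give. For a doubled 4-8 Hz source of 0.1 to 1 times total background power (0.5-100 Hz), at 100 ms and TW = 1:

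| Assumed background | Alpha rise ÷ theta rise |
|---|---|
| 1/f | 1.09-1.25 |
| White | 0.80-0.95 |
| 1/f² | 1.4-2.2 |
| 1/f plus an 18 Hz peak (SD 3 Hz, 0.5-2 times background power) | 0.59-0.98 |
| White plus the same peak | 0.32-0.84 |

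Smooth backgrounds give about 0.8 to 2.2, and a strong beta peak takes the ratio lower. Leakage is substantial in every case, but no single ratio holds.

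**The case against.** The strongest reply is that no analysed outcome has been shown to suffer. The plan gives the estimation of power to the spectral densities, whose segments may be long enough. The statistical summary lists only alpha among the low bands and does not say that it comes from the spectrograms. This stands, and it sets the scope: average alpha power is affected only if it is taken from the 100 ms spectrograms.

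A second reply is that 2.5 Hz was meant as bin spacing. That would explain the number, but the plan says "2.5 Hz frequency resolution". On that reading the word is wrong and the limit on the low bands is unchanged.

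A third is that the band limits are assumed. They are, but delta, theta and alpha are conventionally 3 to 5 Hz wide against a response of 9 to 11 Hz, so modest shifts do not matter. A check with alpha at 8-13 Hz reached the same conclusion.

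Three stronger readings are tempting, and the documents do not support them.

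- A reader might infer that a theta change must appear as an alpha change of at least equal relative size. That holds for a smooth 1/f background but not for a white one, nor for one with a beta peak (step 4), and the documents give no spectrum. In absolute terms theta still receives more of the source than alpha, 34.5% against 24%.
- A reader might infer that the band-power summary as a whole is invalid. The documents do not tie it to the spectrograms, and whole-band beta and gamma are largely kept at 100 ms.
- A reader might extend the point to alpha against low beta. The plan defines no low-beta band, so that pair would rest on a subdivision supplied from outside.

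**Conclusion.** The sentence is wrong as written. The stated window and taper deliver about 10 Hz, not 2.5 Hz, and nothing elsewhere in the documents repairs this. That part follows from the plan's own figures, needs no assumption about sampling rate or signal, and is held with high confidence.

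The consequence is that the listed delta, theta and alpha changes are not reliably separable in the triggered spectrograms. It rests on conventional band limits and on the taper spectrum. No general figure is claimed for the relative size of the false alpha change. Nothing is shown against the spectral densities, or against activity at 200 Hz and above. The error is definite, its effect on interpretation is bounded, and it should be corrected.

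**What to change.** Make the window, taper and resolution agree, and limit band claims to what they resolve. Either route does this.

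- **A. Keep 100 ms.** Restate the resolution as about 10 Hz, make no separate delta, theta or alpha claims from these spectrograms, and take those bands from power spectral densities on longer segments.
- **B. Use a longer window for the low bands.** With one taper, 400 ms gives W = 2.5 Hz. It is not clean for alpha, since 11% of a theta source still lands there, so about 1 s is better where theta and alpha must be told apart. Keep 100 ms for gamma and above.

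It would also help to state the band limits and which estimate supplies average alpha power, but the point does not depend on that.

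**Cost.** A wording change and parameters in an offline script, with no new data. Under B, event timing blurs by about half the window on either side: 200 ms at 400 ms and 500 ms at 1 s. How much that matters depends on episode duration, which the documents do not give. Route A keeps the timing but gives up time-resolved low bands. Some leakage at band edges remains under both.

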# ClinicalTrials.gov Final Outcomes Report

NCT Number:	05103384
Project Title:	Utilizing Neural Signatures and Virtual Reality to Advance DBS Programming
Principal Investigator Name:	[name]
Principal Investigator Organization and Address:	Cleveland Clinic [name]
Document Date:	9/27/2023

**Title:** Utilizing Neural Signatures and Virtual Reality to Advance DBS Programming

**Primary Investigator:** [name]

**Study Funder:** Michael J. Fox Foundation for Parkinson's Research

**Protocol Date:** 9/27/2023

**PROJECT GOAL:** Falls related to postural and gait impairments and freezing of gait (FOG) occur in nearly 80% of Parkinson's disease (PD) patients and are the greatest motor-related contributor to health care costs and the primary reason for transition to dependent care settings among PD patients. Despite their prevalence in the daily lives of PD patients, identifying FOG episodes in a clinical or laboratory environment is challenging. Consequently, the neural signature underlying FOG remains elusive. A necessary step in treating FOG is characterizing neural activity within the basal ganglia during FOG episodes. An approach to evaluate the neural signals associated with FOG includes recording the neural activity in the area of the subthalamic nucleus (STN) or globus pallidus internus (GPi) from implanted deep brain stimulation (DBS) leads. The proposed project combines the most advanced virtual reality (VR) technology and neural recording techniques to identify specific neural correlates of FOG while patients physically walk through a virtual environment, Virtual-Gait Task (V-GAIT), that simulates motor and cognitive\limbic triggers.

**Objective:** To identify the corresponding neural signatures of FOG associated with motor and cognitive\limbic triggers.

Fifteen individuals with PD will complete the V-GAIT modules while synchronized kinematic and neural data from the DBS lead within the STN or GPi are recorded. The kinematic data will be utilized to identify the timing of FOG episodes in the neural data. The neural correlates of FOG in the ON and OFF medication states within each domain will be evaluated.

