## INCLUSION/EXCLUSION CRITERIA

**Participants:** Fifteen individuals with idiopathic PD will be recruited for the study. Individuals who have previously undergone DBS surgery with the Medtronic Percept BrainSense DBS system will complete the protocol while neural data from the DBS electrodes are streamed.

Inclusion Criteria:

- Clinical diagnosis of idiopathic PD
- Previous implantation of Percept DBS system as standard of care for their PD treatment

- Self-reported response of one or greater on question #3 of the FOG-Q
- Ability to ambulate independently for a minimum of 10 minutes
- Ability to provide informed consent

Exclusion Criteria:

- Neurological disease other than PD
- Musculoskeletal impairment that affects one's ability to ambulate for 15 minutes continuously
- Presence of active and untreated psychiatric symptoms meeting Diagnostic and Statistical Manual of Mental Disorders-4th Edition (DSM-IV) criteria for Axis-I disorder. Depression and anxiety are very common in patients with Parkinson's disease and are often mitigated as part of routine care. Depression and anxiety will not preclude study participation
- Cognitive impairment meeting Diagnostic and Statistical Manual of Mental Disorders-4th Edition (DSM-IV) criteria for dementia on formal neuropsychological evaluation
- Current alcohol or substance abuse
- Hearing or visual impairment precluding VR use
- Lack of fluency in English which may invalidate certain tests

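### Does leaving the unit of analysis unstated (trial, event or participant) call for a change to the plan?

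*Combined protocol and SAP*

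**What the plan says.** Under Data Analysis, the steps come in this order. Oscillatory activity is examined around FOG episodes found in the motion-sensor data. "Triggered spectrograms will be calculated for each trial". Changes in power are then related to the kinematically defined events, which are normal walking and FOG. Next, "Power spectral densities will be used to determine the power and confidence bands of oscillatory activity across frequencies during these events". Finally, average band power is described for FOG and for functional walking, and "Within and across participant analyses will determine the degree of consistency and similarity of the neural signal during FOG episodes between each medication state".

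The Percept recording yields "6 electrode pair combinations, 3 combinations per DBS lead". The Neural Recording Procedures instead count six or eight channels, on one or more leads. Entry requires a "Self-reported response of one or greater on question #3 of the FOG-Q", which is a report and not an observed freeze. The Objective covers both targets: "synchronized kinematic and neural data from the DBS lead within the STN or GPi are recorded". Fifteen participants are planned, each with an OFF-medication and an ON-medication session. No test, confidence level or sample-size calculation is given.

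**The concern.** Three units appear (trial, event, participant), and no sentence says which one carries the averages or the bands. A band could describe one recording, the events of one person, all events pooled, or the 15 participants, and these answer different questions. If repeated episodes or correlated electrode pairs were counted as independent observations, a band could be too narrow, and a few frequent freezers could dominate what is presented as a group signature.

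A reader who settles on the participant as the unit still finds three gaps: how six pairs become one value, what happens when a participant has no FOG in one medication state, and whether STN and GPi are shown apart. The bands are the only measure of uncertainty the plan names for its single objective, and these choices could be made after the data are seen.

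**Working it through.** **Reading the steps in order.** A triggered trial is most naturally the epoch around an event. Events are then summarised within a participant, and participants are compared with one another. For a within-participant band, that person's events are the proper unit; for an across-participant band, the participants are. The text names both levels. What it leaves out is the summary step between them.

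**The one derivable figure.** 3 pairs per lead x 2 leads = 6, which agrees with the stated number. The 15 participants cannot be re-derived, because no error rate, effect size or SD is given.

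**Everything below is conditional.** Episode counts, the intraclass correlation (ICC), skew and freezing rates are assumptions; the documents give none of them. Coverage refers to a nominal 95% interval, and formula coverage is 2Φ(1.96/√R) - 1, where R is true variance divided by naive variance.

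1. *Mean in one condition, all events pooled.* R = 1 + (m - 1) x ICC for m events per person. With m = 10 and ICC 0.3, R = 1 + 9 x 0.3 = 3.7, the effective n is 150/3.7 = 40.5, and coverage is 69%. Over m = 5 to 20 and ICC 0.1 to 0.7, coverage runs from 90% down to 40%.

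2. *FOG minus walking, equal counts, constant effect.* The person's own level cancels, so R = 1 - ICC. ICC 0.2 gives 97.2% and ICC 0.5 gives 99.4%, so pooling is conservative. Simulation gives 96.8-99.3%.

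3. *As in 2, but the effect varies between people (variance 0.1, total variance 1).* With m = 20 and ICC 0.2, the naive variance is 2/300 = 0.0067 and the true variance is 1.6/300 + 0.1/15 = 0.0120. R = 1.8 and coverage is 86%. Simulation over all settings gives 86-98%.

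4. *Skewed FOG counts.* Suppose one person has 40 episodes and 14 have 4 each (96 in all), so that the first supplies 40/96 = 42%. The sum of squared weights is 0.198, equivalent to 1/0.198 = 5.1 equally contributing people. The naive variance is 2/96 = 0.0208.
   - If 96 walking periods are spread evenly, the person's level no longer cancels. True variance = 2(1 - ICC)/96 + ICC x (0.198 - 1/15). At ICC 0.5 this is 0.0104 + 0.0656 = 0.0760, so R = 3.65 and coverage is 70%.
   - If each person's walking periods match their episodes in number, the last term vanishes, R = 1 - ICC again, and coverage is 97-99%.

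   Simulation with negative binomial counts (k = 0.5, mean 5 to 20) shows the same split. With fixed walking counts, coverage is 45-88%. With matched walking counts it is about 96-99% for a constant effect and about 72-91% with effect variance 0.1. A paired participant-level interval covers 94-96% with equal counts and with skewed counts against fixed walking counts.

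5. *ON minus OFF during FOG, the comparison the plan does name.* With skewed counts and half as many episodes ON as OFF, event-level coverage is 94-96% for a constant effect and 76-90% with effect variance 0.1.

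6. *Six pairs counted as six observations.* R = 1 + 2 x (within-lead correlation) + 3 x (between-lead correlation). Correlations of 0.5 and 0 give R = 2 and 83%; 0.9 and 0.5 give R = 4.3 and 66% (64% in small-sample simulation). Six separate intervals have at most a 1 - 0.95^6 = 26.5% chance that one or more excludes zero with no true effect if pairs are uncorrelated, and 15-24% if they are correlated. The plan states no excludes-zero rule.

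7. *Empty cells.* Under k = 0.5 the chance of no OFF-state episode is (0.5/(0.5 + m))^0.5, which is 30% at m = 5 and 16% at m = 20, so skew builds in empty cells. A median of 8-11 of 15 then freeze in both states, against 14-15 if all share one rate.

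8. *Splitting by target.* The 95% half-width for a participant-level mean is t(0.975, n - 1)/√n: 0.55 SD at n = 15, 0.77 at n = 9 and 1.24 at n = 5.

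**The case for a change.** The best case for changing the plan is that calling the analysis descriptive does not dispose of the matter. Confidence bands are promised, and a band cannot be read without its unit. Naming two levels of analysis does not say which one the bands use, and the Confidentiality section brings in biostatistics only where appropriate, so no rule comes from there. The Project Goal itself says that FOG is hard to identify in a clinic or laboratory, so empty ON or OFF cells are a realistic prospect. Settling the matter in advance would take a few sentences and no new data.

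Much of this stands. The unit, the pair rule and the empty-cell rule are absent, and someone reading the results will need to be told what was done. Item 1 shows that pooling all events for a one-condition band would always narrow it.

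Three things do not stand. First, the text plans no pooling; a participant-level analysis fits it fully. Second, the alarming figures rest on a combination that the documents do not establish, namely highly skewed FOG counts with the same number of walking periods for everyone, and on a FOG-minus-walking interval that the plan does not name. Third, the remedies are not all gains. Separate STN and GPi results would split at most 15 people by an unknown ratio and could more than double the half-width, as item 8 shows. The two channel descriptions may differ only in terminology, since one counts channels and the other counts pair combinations. The worry about empty cells must also be set against a task built to trigger freezing and a first session with both DBS and medication off.

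**Conclusion.** No change follows. The plan leaves out detail that an analyst fills in the ordinary way: events as the unit within a person, and one value per person per condition (or a model with participant effects) across people. No stated rule conflicts with that, and none yields a wrong answer.

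Harm would arise only if events or pairs were pooled as independent, and even then its direction varies. For the FOG-minus-walking difference, pooling is conservative (97-99% coverage) with equal counts and a constant effect, and seriously anti-conservative (45-88%) with skewed FOG counts against fixed walking counts. Variation in the effect between people gives intermediate values: 86-98% with equal counts and about 72-91% with skewed but matched counts. All of this rests on assumed episode counts, correlations and skew. Because no test is planned, what is affected is the width and meaning of the bands, not a type I error rate. Reporting the targets separately is a fair trade-off at this sample size, not a correction.
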